6.6.7.5. Time to Discontinuation

Same Cox proportional hazard model as in section 6.6.3.2 will be performed with country (ie, France, Germany and United Kingdom) and age group at randomization (ie, age ≤ 3.0 months, age > 3.0 to ≤ 6.0 months, age > 6.0 months) as the covariates.

For the analysis by country, only age group at randomization will be used as covariates as described in section 6.6.6.2.2.

Kaplan-Meier Plots will be provided for time to discontinuation from the study (overall and by country). P-value from Log Rank test will be provided.

6.6.7.6. Social Deprivation Index (SDI)

Social Deprivation Index (SDI) based of postal code will be summarized by country (if feasible) (Taha and al¹¹). Incidence of RSV LRTI hospitalization will be summarized by the social deprivation index in each country. Descriptive statistics will be provided. SDI data will also be listed.

For each country, postal code collected in the eCRF will be merged with official data from each country official website (France^{12, 13}, United Kingdom^{14, 15}, Germany¹⁶) uploaded in SAS in order to get the the SDI (numeric or decile) of the city of each participant:

- For France, second column named “Code Postal” from *correspondance-code-insee-code-postal.xls* document will be used first to get the code from Institut National de la Statistique des Etudes Economiques (INSEE).

Then, *inserm_fdep_com_metropole_j.xls* document will provide the corresponding numeric SDI in column named “t1_fdep09”. This will be derived in deciles from 1 to 10 using SAS procedures.

When, in the first tracker, a postal code corresponds to several INSEE codes, the following steps to derive a unique decile will be performed:

- Select all INSEE codes corresponding to the postal code
 - Merge with *inserm_fdep_com_metropole_j.xls* by INSEE code (“Code INSEE” with “c_insee_com”) and Commune Code (“Code Commune” with “c_code_comm”)
 - Compute a weighted average of the fdep09 index (t1_fdep09 column), weighing on the number of inhabitants for each town (variable t1_p09_pop in the tracker)
 - Convert the obtained average index into deciles following the rule above.
- For the United Kingdom, *File_1_-_IMD2019_Index_of_Multiple_Deprivation.xls* will provide the SDI (from column named “Index of Multiple Deprivation (IMD) Decile”) corresponding to the collected postal code.
PCD_OA_LSOA_MSOA_LAD_NOV22_UK_LU.xls, from the Office for National Statistics will be used to do the link between the collected postal code and the Lower Super Output Area (LSOA) code used to get the SDI.
 - For Germany, column named “GISD10_2012” from *GISD_PLZ5_2014.xls* will provide the SDI which corresponds to the collected postal code.

In case of missing or invalid postal code, participants will not be considered in the analysis.

6.6.7.7. RSV LRTI Hospitalization through the RSV Season in the Subset of Neonate Participants

Same analysis as for the primary efficacy analysis of the primary endpoint in Section 6.6.1 will be conducted in the subset of neonate participants.

6.6.7.8. Follow-up

Number and percentage of participants will be provided for:

- Monthly responses in eDiary according to the analysis window in Section 5.1.4.

In addition, at the time of First Year Analysis, follow-up time in months will be described for all participants (based on the primary endpoint RSV LRTI Hospitalizations), participants with RSV LRTI Hospitalizations, participants with Very Severe RSV LRTI, participants with Hospitalizations for all-cause LRTI at the following timeframes (see Section 6.1 for details on the descriptive statistics):

- Through the RSV Season (overall and in each country)
- Through Day 151 post-dosing/randomization (overall and in each country)
- Through Day 181 post-dosing/randomization (overall and in each country)
- From 181 days post-dosing/randomization to 366 days post-dosing/randomization in participants with no event before Day 181 (overall and in each country, excluding participants with very severe RSV LRTI)

Follow-up time in months will also be summarized at the time of Second Year analysis:

- From 366 days post-dosing/randomization to 731 days post-dosing/randomization in UK reconsented participants. However, this will not be summarized for subgroup of participants with Very Severe RSV LRTI.
- From 366 days post-dosing/randomization to 511 days post-dosing/randomization in UK reconsented participants. However, this will not be summarized for subgroup of participants with Very Severe RSV LRTI.
- From 512 days post-dosing/randomization to 731 days post-dosing/randomization in UK reconsented participants. However, this will not be summarized for subgroup of participants with Very Severe RSV LRTI.
- Through Day 511 post-dosing/randomization in UK reconsented participants. However, this will not be summarized for subgroup of participants with Very Severe RSV LRTI.
- Through Day 731 post-dosing/randomization in UK reconsented participants. However, this will not be summarized for subgroup of participants with Very Severe RSV LRTI.
- Through Day 366 post-dosing/randomization in UK reconsented participants (recurrent wheeze event)
- From Day 366 post-dosing/randomization to Day 731 post-dosing/randomization in UK reconsented participants (recurrent wheeze event)
- Through Day 731 post-dosing/randomization in UK reconsented participants (recurrent wheeze event)

6.6.7.9. Efficacy Events in Participants who Received Beyfortus as a Routine Medication

At the time of First Year Analysis, number and percentage of participants with efficacy events through the RSV Season will be provided, among participants who received Beyfortus as a routine medication:

- RSV LRTI Hospitalizations
- Very Severe RSV LRTI
- All-Cause LRTI.

Same table will be produced for the below timeframes:

- Through Day 151 Post-Dosing/Randomization
- Through Day 181 Post-Dosing/Randomization
- From 181 Days Post-Dosing/Randomization to 366 Days Post-Dosing/Randomization in participants with no event before Day 181 (excluding Very Severe RSV LRTI event)

At the time of Second Year Analysis, table will be repeated for the timeframe “from 366 Days Post-Dosing/Randomization to 731 Days Post-Dosing/Randomization” (excluding Very Severe RSV LRTI event) in the UK reconsented participants.

All above tables will be produced only if there are at least 10 participants who received Beyfortus as a routine medication during the study.

6.6.7.10. Rerun of Primary Analysis at the Time of First Year Analysis

The Primary Analysis will be re-run at the time of the First Year Analysis considering the same cut-off date and the same rules as the Primary Analysis.

6.6.8. Subgroup Analyses

Various subgroup analyses of the efficacy data will be reported. These analyses will investigate the treatment response within specific subgroups of interest, and assess whether the treatment response is consistent across different subgroup levels. All analyses will be performed on the All Randomized Set without imputation.

6.6.8.1. Subgroup Analyses for the Primary Endpoint (RSV LRTI Hospitalization through the RSV Season)

The following subgroup analyses are of interest for the primary endpoint, the incidence of RSV LRTI hospitalization through the RSV season in healthy term and preterm infants in all 3 countries combined:

- Age group at randomization: age \leq 3.0 months, age $>$ 3.0 to \leq 6.0 months, age $>$ 6.0 months
- Weight at randomization: weight $<$ 5 kg, weight \geq 5 kg
- Gestational age: $<$ 37 weeks, \geq 37 weeks
- Sex: male, female
- Infants dosed in season (dosed on or after the start date of RSV season) or before the start of the RSV season
- Infants born in season (born on or after the start date of RSV season) and before the start of the RSV season

The subgroup analyses will be conducted as for the primary efficacy analysis of the primary endpoint in Section 6.6.1.

For all these subgroup analyses, forest plots will be provided.

6.6.8.2. Subgroup Analyses for the First Secondary Endpoint (Very Severe RSV LRTI through the RSV Season)

The following subgroup analyses are of interest for the first secondary endpoint, the incidence of the very severe RSV LRTI through the RSV season:

- Age group at randomization: age \leq 3.0 months, age $>$ 3.0 to \leq 6.0 months, age $>$ 6.0 months
- Weight at randomization: weight $<$ 5 kg, weight \geq 5 kg
- Gestational age: $<$ 37 weeks, \geq 37 weeks
- Sex: male, female
- Infants dosed in season (dosed on or after the start date of RSV season) or before the start of the RSV season
- Country: France, Germany, United Kingdom

The subgroup analyses will be conducted as for the primary efficacy analysis of the first secondary endpoint in Section 6.6.4.1.

For all these subgroup analyses, forest plots will be provided.

6.6.8.3. Subgroup Analyses of RSV LRTI Hospitalization through Day 151 Post-Dosing/Randomization

The following subgroup analyses are of interest for RSV LRTI hospitalization through Day 151 days post-dosing/randomization using the similar methods to that described in Section 6.6.4.3:

- Age group at randomization: age ≤ 3.0 months, age > 3.0 to ≤ 6.0 months, age > 6.0 months
- Weight at randomization: weight < 5 kg, weight ≥ 5 kg
- Infants dosed in season (dosed on or after the start date of RSV season) or before the start of the RSV season
- Infants born in season (born on or after the start date of RSV season) and before the start of the RSV season

For all these subgroup analyses, forest plots will be provided.

6.6.8.4. Subgroup Analyses of RSV LRTI Hospitalization through Day 181 Post-Dosing/Randomization

The following subgroup analyses are of interest for RSV LRTI hospitalization through Day 181 post-dosing/randomization:

- Age group at randomization: age ≤ 3.0 months, age > 3.0 to ≤ 6.0 months, age > 6.0 months
- Weight at randomization: weight < 5 kg, weight ≥ 5 kg
- Infants dosed in season (dosed on or after the start date of RSV season) and before the start of the RSV season
- Infants born in season (born on or after the start date of RSV season) and before the start of the RSV season

For all these subgroup analyses, forest plots will be provided.

6.6.9. Post-hoc Analyses

In the context of the VAS00006 study (for which the objectives of interest stated in the study protocol are to assess the efficacy of nirsevimab in preventing RSV LRTI hospitalization, very severe RSV LRTI, all-cause LRTI compared to no intervention), there is a need to conduct a post-hoc analysis, for a less specific outcome in order to assess the risk reduction in all-cause hospitalizations associated with nirsevimab and describe in specific timepoints, the incidence of RSV LRTI hospitalization and all-cause LRTI hospitalization in UK reconsented participants during the study.

Additional objectives for the post-hoc analysis:

- To assess the relative risk reduction (i.e., efficacy) in all-cause hospitalizations associated with nirsevimab compared to no intervention.
- To describe in each treatment group the incidence of RSV LRTI hospitalization and all-cause LRTI hospitalization in UK reconsented participants during the study.

Additional endpoints for the post-hoc analysis:

- Incidence of all-cause hospitalization, overall and in each country
 - Through the RSV season, through 150 days post-dosing/randomization, through 180 days post-dosing/randomization, from 181 days post-dosing/randomization to 366 days post-dosing/randomization,
 - Through the end of year 2022.
- Incidence of RSV LRTI hospitalization, in UK reconsented participants
 - From 366 days post-dosing/randomization to 511 days post-dosing/randomization, from 512 days post-dosing/randomization to 731 days post-dosing/randomization, through 511 days post-dosing/randomization, through 731 days post-dosing/randomization.
- Incidence of all-cause LRTI hospitalization, in UK reconsented participants
 - From 366 days post-dosing/randomization to 511 days post-dosing/randomization, from 512 days post-dosing/randomization to 731 days post-dosing/randomization, through 511 days post-dosing/randomization, through 731 days post-dosing/randomization.

6.6.9.1. Incidence of All-cause Hospitalization, Overall and in Each Country

Hospitalizations are counted from the LRTI forms and the Adverse Event forms in the CRF. Participants with at least one hospitalization registered in any of those forms are considered. The relative risk reduction (i.e., efficacy) in all-cause hospitalizations associated with nirsevimab compared to no intervention is measured as described in section 6.6.1, and the same rules apply for the follow-up time, taken into consideration the dates for hospitalizations recorded in the LRTI forms and Adverse Event forms.

Analyses for the above all-cause hospitalization endpoints will be performed only at the time of First Year Analysis, except through the end of year 2022 endpoint that will be performed only at the time of Second Year Analysis.

For through the end of year 2022 endpoint, participants who do not have any all-cause hospitalization will be censored on 31st December 2022 or last available date for no event of interest whichever is earlier.

For participants who discontinued from the study before 31st December 2022, the end date for the efficacy follow-up will be the date of the last available date with confirmation of no efficacy endpoints of interest.

For participants who had no contact for safety events at all, the end date will be the start date (date of randomization for participants randomized to no intervention / date of immunization

for participants randomized to nirsevimab and treated / date of randomization for participants randomized to nirsevimab but not treated).

Notes:

- If efficacy endpoint-related events occur after 31st December 2022, they will not be considered and the end date will be 31st December 2022.
- If a participant receives Beyfortus as part of a routine immunization, any efficacy endpoint-related events occurring after Beyfortus immunization will not be considered and the end date will be the date of injection of Beyfortus.

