To describe in each study group the incidence of RSV LRTI hospitalization and all-cause LRTI hospitalization in UK reconsented participants from D366 to D731	 Incidence of RSV LRTI hospitalization Incidence of hospitalization for all-cause LRTI 				

Overall Design

Type of design	Open-label, multi-center, parallel 2-arm study: nirsevimab compared to no preventive RSV intervention					
Phase	IIIb					
Control method	Comparison to no preventive intervention					
Study population	Healthy infants born ≥ 29 weeks gestational age (WGA) entering their first RSV season and not eligible for palivizumab (born either in-season or out-of-season)					
Countries	France, Germany, and the United Kingdom					
Level and method of blinding	Open-label					
Study intervention assignment method	 Randomization will be stratified by the following: Country Age group at time of randomization (ie, age ≤ 3.0 months, age > 3.0 to ≤ 6.0 months, age > 6.0 months) 					

Brief Summary

The purpose of this study is to determine the efficacy and safety of a single intramuscular (IM) dose of nirsevimab, compared to no intervention, for the prevention of hospitalizations due to

LRTI caused by confirmed RSV infection (henceforth referred to as RSV LRTI hospitalizations) in all infants under 12 months of age who are not eligible to receive palivizumab.

Study Duration: 12 months post-dosing/randomization for France, Germany, and UK non-reconsented participants, 24 months post-dosing/randomization for UK reconsented participants. D01 will be the day of randomization (both study groups) and immunization (nirsevimab group).

Treatment Duration: 1 IM injection

Study Calendar:

- Planned date of first participant in: 01 September 2022
- Planned date of last participant in: 28 February 2023
- Planned date of last visit last participant: 28 February 2025

Note: As much as operationally feasible, the date of inclusion of the first participant will be aligned with the beginning of the RSV season. It is thus possible that the first participants are enrolled earlier than 01 September 2022.

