 - for the participants who had no contact for safety events at all throughout the efficacy follow-up period, the end date for the efficacy follow-up will be date of randomization for participants who are randomized to no intervention, the date of treatment dosing for participants who are randomized to nirsevimab and treated, and the date of randomization for participants who are randomized to nirsevimab but not treated.

The total person-time for the follow-up time of each participant will be calculated as:

Person-months = (the end date - the start date + 1)/30.4375.

NN (days), the total person-time contributed by participants randomized in the nirsevimab, will be the sum of person-months for all the participants in the nirsevimab group. And NC (days), the total person-time contributed by participants randomized in the no intervention group, will be the sum of person-months for all the participants in the no intervention group.

The 2-sided 95% CI for the efficacy will be calculated by an exact method assuming a binomial distribution of the number of RSV LRTI hospitalizations in the nirsevimab group conditional on the total number in both groups (described by Breslow and Day⁷) accounting for the follow-up time post-dosing/randomization.

The superior efficacy of nirsevimab in preventing RSV LRTI hospitalization is concluded if the lower bound of 2-sided 95% CI of the efficacy is $> 0\%$. P-value will also be provided. The primary efficacy analysis of the primary endpoint will be performed with the All Randomized Set.

RSV season is the period of increased RSV infection. For the purpose of efficacy analyses, the start of the RSV season will be defined on a country-by-country basis and will be based on country-specific epidemiological surveillance and the cut-off date (28Feb2023, except for site parent contact and medical call center contact, for which the date of database lock for Primary Analysis will be used) will be used as end dates.

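### The post-hoc end-of-2022 all-cause hospitalization endpoint is not limited to infants who started by 31 December 2022, so later starters can receive zero or negative person-time

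*SAP*

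**What the plan says.** SAP 6.6.9 lists, among its post-hoc endpoints, the incidence of all-cause hospitalization up to the end of 2022, overall and by country. SAP 6.6.9.1 schedules this endpoint for the Second Year Analysis only and takes its method and follow-up rules from SAP 6.6.1. Its end-date rules are:

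- Event-free infants: "participants who do not have any all-cause hospitalization will be censored on 31st December 2022 or last available date", whichever comes first.
- Events after the window: "they will not be considered and the end date will be 31st December 2022".
- Early discontinuation, where the rule opens "For participants who discontinued from the study before 31st December 2022, the end date for the efficacy follow-up will be the date" and goes on to name the last date confirmed event-free.
- No contact: "For participants who had no contact for safety events at all, the end date will be the start date".
- Routine Beyfortus: follow-up ends at the injection.

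SAP 6.6.1 starts the clock at randomization, or at dosing for treated nirsevimab infants. It computes "Person-months = (the end date - the start date + 1)/30.4375", sums this over each arm, and uses the All Randomized Set. The protocol calendar (Section 1.1) gives "Planned date of first participant in: 01 September 2022" and "Planned date of last participant in: 28 February 2023". SAP 6.6.9.1.1 adds a Poisson sensitivity model based on SAP 6.6.2.1, whose offset is the log of follow-up time, with a negative binomial model as a possible alternative.

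**The concern.** The window closes 59 days before the planned end of enrolment, yet the analysis set is everyone randomized. An infant who joins in January or February 2023 was never at risk inside the window and cannot contribute an event to it. The end-date rule nevertheless assigns such an infant an end date before the start date, and the formula has no floor at zero.

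The problem does not arise in SAP 6.6.1 itself. There the cut-off is 28 February 2023, the same day as planned last participant in, so on the planned calendar an infant followed to the cut-off has at least one day. Moving the cut-off to 31 December 2022 removes that protection. For other windows the SAP does define who is at risk: SAP 6.6.4.3.5, 6.6.4.3.6 and the later-window analyses in 6.6.9.2.1 limit the analysis to infants without the event before the window opens. No comparable restriction appears here.

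At stake are the per-arm incidence rates of a listed endpoint, overall and by country, and the consistency of the main and sensitivity analyses.

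**Working it through.** The documents state no figure for this endpoint, so there is none to reproduce. The check applies the SAP's own formula.

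**Inputs.** Window end 31 December 2022 (SAP 6.6.9.1); formula and start date (SAP 6.6.1); planned enrolment 1 September 2022 to 28 February 2023 (Protocol 1.1); allocation 1:1 (Protocol 6.3.1). The share enrolled in 2023, called f, is not stated and is an assumption.

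**Step 1: person-time by start date.** Days = 31 Dec 2022 - start + 1, for an infant with contact and no event in the window.

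| Start | Days | Person-months (days/30.4375) |
|---|---|---|
| 1 Sep 2022 | 122 | 4.01 |
| 31 Dec 2022 | 1 | 0.03 |
| 1 Jan 2023 | 0 | 0 |
| 2 Jan 2023 | -1 | -0.03 |
| 31 Jan 2023 | -30 | -0.99 |
| 28 Feb 2023 | -58 | -1.91 |

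A 2023 starter hospitalized in 2023 gets the same values, because the event is ignored and the end date is set to 31 December 2022. A 2023 starter with no contact has end = start, hence +1 day, which also lies outside the window.

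**Step 2: effect on the rates if the values are summed.** Assume one infant per day over the planned 181 days.

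- 2022 starters: 122 days, 1 + 2 + ... + 122 = 122 x 123/2 = 7,503 infant-days, mean 61.5.
- 2023 starters: 59 days, -(0 + 1 + ... + 58) = -(58 x 59/2) = -1,711 infant-days, mean -29.
- Literal total: 7,503 - 1,711 = 5,792. The numerator is unchanged, so each arm's rate is multiplied by 7,503/5,792 = 1.295.

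For a general share f, with uniform accrual within each period:

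factor = 61.5(1 - f) / [61.5(1 - f) - 29f]

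| Assumed f | Factor |
|---|---|
| 1% | 60.885/60.595 = 1.005 |
| 5% | 58.425/56.975 = 1.03 |
| 10% | 55.35/52.45 = 1.06 |
| 20% | 49.2/43.4 = 1.13 |
| 59/181 = 32.6% (uniform) | 1.30 |

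**Step 3: effect on efficacy.** With g(f) = 61.5(1 - f) - 29f and h(f) = 61.5(1 - f), the literal rule multiplies the rate ratio by [g(fC)/g(fN)] / [h(fC)/h(fN)], where fN and fC are the 2023 shares in the nirsevimab and no-intervention arms. Equal shares give 1.000. Shares of 9% (nirsevimab) and 11% (no intervention) give 0.988, and the reverse gives 1.012.

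**Step 4: sensitivity model.** The log of zero or of a negative number is undefined, so the Poisson or negative binomial model cannot use these infants as specified. The exact method would still sum them if the formula is followed literally.

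**The case against.** The strongest reply is that the endpoint's name makes the intention plain: an infant not yet randomized has no follow-up in 2022, and a competent programmer would drop such infants or set their time to zero. There would then be no inflation. This stands as a limit on the consequence, which depends on negative values actually being summed. It does not remove the gap, because the SAP does not say which handling applies.

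Several stronger readings are tempting, and the documents do not support them.

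- *That every infant gets 31 December 2022 as end date.* Early discontinuation, no contact and routine Beyfortus have their own end dates, and an infant with an event inside the window ends at admission. The defect concerns 2023 starters.
- *That the rates are inflated by 30%.* That figure needs both uniform accrual and summation of negatives. The calendar dates are planned ones, the protocol allows enrolment before 1 September 2022, and no monthly or country accrual is given. Protocol 4.2 and 10.1.3 suggest that many infants born out of season would be enrolled around season start, although in-season births would come later. The share could be small.
- *That efficacy is biased.* Randomization gives both arms nearly the same 2023 share, so the ratio barely moves (Step 3).
- *That the sensitivity model will silently drop infants.* The documents do not say how the program treats a non-positive time. If it did drop them, that model would in effect be analysing the right set.

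Finally, SAP 6.6.9.1.1 labels the analysis post-hoc, bars p-values and says that no statistical conclusion should rest on it alone. That is correct and limits the severity.

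**Conclusion.** The gap is real and minor. As written, SAP 6.6.9.1 combined with SAP 6.6.1 gives 0 to -58 days to infants who start in January or February 2023 and have contact, and +1 day outside the window to those with no contact. If these values enter the sums, both arms' incidence rates are overstated by a factor between about 1.005 (1% of infants enrolled in 2023) and 1.30 (32.6%, uniform accrual). The range rests on an assumed share and on accrual being even within each period, and it ignores the other end-date rules. A country with a larger 2023 share would be affected more, but the documents do not show whether any country had one. The main and sensitivity analyses could also rest on different sets. The relative risk reduction is essentially unchanged, and no primary, key secondary or other confirmatory result is touched.

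**What to change.** Add one sentence to SAP 6.6.9.1: the end-of-2022 endpoint is analysed in participants whose start date (randomization, or dosing if randomized to nirsevimab and treated) is on or before 31 December 2022, and participants who start later contribute neither events nor person-time. Apply the same restriction to the reported N and to the Poisson or negative binomial sensitivity model, overall and by country.

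The cost is one sentence and one filter in the program. No valid event or time at risk is lost, since later starters have neither inside the window. The only downside is a smaller stated N for this endpoint. The post-hoc section entered the SAP in version 6.0 (14 January 2025), well after planned enrolment ended, so the actual start dates should be available to apply the filter.
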